Data are stored on secure servers and managed in accordance with Swedish and European data protection and privacy legislation. Treatment is provided via the routine care online treatment platform of Region Stockholm (“Stöd- och behandlingsplattformen”, SOB) which requires electronic identification and relies on encrypted traffic. Electronic records are also kept in a secure data system, as is required by law, and in accordance with SLSO guidelines. For the purpose of this study, a separate online measurement platform is used, with data stored on secure servers managed by Karolinska Institutet on behalf of Liljeholmen primary care clinic (“personuppgiftsbiträdesavtal”). This measurement platform has been used in several previous clinical trials of internet-delivered treatment, see for example EPM ethics applications 2019-04816 and 2020-01740. All trial applicants are required to log in to the measurement platform with electronic identification, and subsequent communication relies on encrypted traffic and two-factor authentication (a personal password + unique SMS codes).

Clinicians who deliver treatments in the context of this trial are only permitted access to those online treatments for which they are responsible. Likewise, on the measurement platform, patients' weekly measurements of somatic symptoms and symptom preoccupation can be monitored by each respective therapist so as to facilitate conventional adaptation of clinical interventions (as is done in routine care), but the extraction of outcome data for the purpose of research (all of Table 1, all participants) is only made available for researchers of the trial and one research assistant. All datasets are pseudonymized by means of a built-in function on the measurement platform, stored on secure servers, and not together with information that allows for individuals to be re-identified. Such information (“kodnyckeln”) is stored separately, exclusively in encrypted form, and is solely accessed by the researchers and the assistant of the trial. Results are published and conveyed in a way that does not allow for the identification of any participant. In accordance with SLSO guidelines, 10 years after the last publication, original datasets and information necessary for individuals to be identified (“kodnyckeln”) are deleted and key documentation from the trial is transferred to long-term storage in the Region Stockholm archive.

Conditions

Both conditions involve structured content that is delivered via the secure routine care text-based treatment platform (SOB, see above) over the 10-week main phase. In both conditions, patients are given a personal account to the SOB to which they may log in at any time.

Flexible internet-delivered exposure-based treatment

The flexible exposure-based treatment protocol was written by [name] for a previous feasibility trial at Karolinska Institutet, Stockholm, Sweden (ClinicalTrials.gov identifier NCT04511286). In this treatment, the patient completes the equivalent of 5 book chapters with homework exercises, and communicates with a therapist via an email-like system. The therapist is either a licensed psychologist or a mental health clinician with adequate training in psychotherapy under supervision that replies to messages from the patient within 48 hours except during weekends. Exposure exercises are tailored to the needs of the particular patient. The initial phase of treatment incorporates education about how psychological factors can contribute to somatic symptom distress, functional impairment, and overall symptom burden. The patient is encouraged to survey his or her own reactions to physical symptoms and attempt to refrain from strategies aimed at short-term reduction in symptoms and related distress (response prevention). The following modules encourage the patient to work with tailor-made exposure exercises in various ways. The treatment is thus similar to several previously evaluated protocols intended specifically for functional somatic syndromes

Exposure-based treatment vs. standardized education for distress related to somatic symptoms Study protocol intended for peer review

including fibromyalgia (4) and irritable bowel syndrome (5) or chronic health conditions such as asthma (3) and atrial fibrillation (12).

Standardized routine care education and prolonged assessment control

Patients randomized to the standardized education and prolonged assessment condition are provided with standardized routine care educational material about the management of psychological distress and somatic symptoms, as available via the national 1177.se service. Via email-like messages on the treatment platform, patients also receive basic emotional support by a clinician who encourages the patient to (1) adhere to standardized routine care guidelines for the management of distress and symptoms, (2) make use of regular health care services, and (3) monitor symptoms and wellbeing on a weekly basis. After the post-treatment assessment, participants in the control condition are crossed over to the tailored exposure-based treatment. In other words, all participants of the randomized controlled trial are offered to take part in exposure-based treatment for distress related to somatic symptoms.

As to the choice of control condition, it is important to recognize that while there exists no standout reference standard treatment for patients with distress related to somatic symptoms, the most common practice in primary care is probably that of offering support and promoting healthy lifestyle behaviors such as physical exercise, a healthy diet, and regular recuperating behaviors (8, 32). We thus expect the standardized routine care education and prolonged assessment control to produce effects similar to those typically resulting from support given in routine care, for example by the individual general practitioner.

Statistical analysis

The analysis plan here described will be pre-registered as part of this study protocol. Multiple imputation will be based on the following predictors: time, age, gender, screening somatic symptoms, screening symptom preoccupation, treatment adherence, and missing data rate. This will be done separately for each condition (exposure vs. control) so as to maintain group-specific interactions. Change in the primary outcome measure (PHQ-15) and other continuous scales will be analyzed using multilevel regression models (33) with patient at level 2, using an autoregressive (AR(1)) covariance structure, fitted by maximum likelihood. Longitudinal outcomes will be modelled intention-to-treat, with time, group (exposure vs. control), and the time \times group interaction as predictors ($\alpha=5\%$). As the feasibility trial was indicative of a curvilinear effect of time (unusual in the field), the inclusion of a time \times time interaction will also be considered based on model fit. The primary statistical test is that of the coefficient for the time \times group interaction pertaining to a group difference in average change in the PHQ-15 over the main phase of the trial, i.e., from pre- to post-treatment. Standardized mean effects are conceptualized as the time \times group interaction divided by the endpoint standard deviation. Long-term effectiveness is modeled using piecewise regression models, with a spline at post-treatment. Response rates are also explored in terms of clinically significant change (34). The following putative moderators will be explored based on time \times group \times moderator interactions: age, gender (if adequate power), screening somatic symptoms, and screening symptom preoccupation. Explorative secondary analyses will also focus on change in each somatic symptom domain of the PHQ-15 (pain, gastrointestinal, cardio-pulmonary, fatigue) as well as specific functional somatic syndromes and chronic health conditions if the number of patients in each condition is at least 5. Cost-effectiveness analysis is based on the incremental cost-effectiveness ratio (ICER) and focuses on a societal perspective, with resource use derived from the TIC-P and sensitivity analyses based on cluster bootstrapping (35). Mediation analysis is based on latent growth modelling (36), and random-intercepts cross-lagged panel models (37) to assess temporal superiority, i.e., whether change in putative mediators

Exposure-based treatment vs. standardized education for distress related to somatic symptoms Study protocol intended for peer review

systematically precede change in outcomes on a week-by-week basis. We will also test the hypothesis that men are more inclined than women to seek health care for somatic symptoms when they are in fact suffering from a psychiatric condition, as based on a 2x2 χ^2 test of exclusions due to other principal psychiatric conditions vs. other factors, men vs. women.

Time schedule as of February 2021

After approval from the Swedish Ethical Review Authority this project is scheduled to be completed in approximately 3 years, beginning with the education of personnel over the first half of 2021. Recruitment is expected to begin around the summer of 2021. We expect to recruit approximately 50-80 patients per year, which implies that recruitment will be complete around the middle of 2023. We expect the last follow-up assessment, and writing of the primary journal article to take place around mid-2024. Results will be communicated via peer reviewed scientific journal articles.

Research group

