- Compared to the control condition, does flexible internet-delivered exposure-based treatment lead to a larger improvement in symptom preoccupation, psychiatric symptom burden, and functional impairment? Hypothesis: Yes.
- In flexible internet-delivered exposure-based treatment, are effects maintained up to 12 months after treatment? Hypothesis: Yes.
- Is flexible internet-delivered exposure-based treatment cost-effective compared to the control condition? Hypothesis: Yes.
- Is the controlled effect of the flexible exposure-based treatment on self-rated somatic symptoms moderated by baseline symptoms and preoccupation? Hypothesis: Yes.
- Is the effect of the flexible exposure-based treatment on self-rated somatic symptom burden mediated by a reduction in symptom preoccupation? Hypothesis: Yes.

Methods

Design and power

Randomized controlled trial of flexible internet-delivered exposure-based treatment for distress related to somatic symptoms, based at Liljeholmen academic primary care clinic, Stockholm, Sweden. Patients (N=160) who report being bothered by somatic symptoms (and who may or may not meet criteria for a diagnosis where distress related to symptoms is common, such as fibromyalgia or asthma), who express interest in psychological treatment, and who's medical status does not make exposure therapy unsuitable are randomized (1:1), in consecutive even numbered cohorts, to flexible internet-delivered exposure-based treatment or an internet-delivered standardized education control. The trial is powered to enable the study of moderate between-group effects ($d=0.5$) as based on mean tests with 80% power, given $\alpha=0.05$ and up to 20% data loss.

Eligibility criteria

- a) (i) Either much bothered by at least one somatic symptom (2 points on at least one item of the PHQ-15) or at least a moderate overall somatic symptom burden (PHQ-15 sum 10 points (16)), with (ii) recurrent distress related to somatic symptoms ≥ 4 months
- b) Symptoms not best explained by, and clinical picture not dominated by, severe health anxiety (where an established treatment already exists (17)) or a non-somatoform psychiatric disorder such as depression, panic disorder, primary insomnia, or a chronic stress disorder
- c) Affirms that he or she is interested in completing an intense psychological treatment with the aim of reducing distress associated with physical symptoms
- d) Adult (≥ 18 years old)
- e) Living in Stockholm County
- f) Can read and write in Swedish

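### The primary and imputation models omit the cohorts within which patients are randomised, which costs a little precision if cohorts differ in their rate of PHQ-15 change

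*Combined protocol and SAP*

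**What the plan says.** The protocol's Design and power section says that patients are "randomized (1:1), in consecutive even numbered cohorts". It states neither the number nor the size of the cohorts. The planned total is 160, sized for d = 0.5 at α = 0.05, "as based on mean tests with 80% power" and allowing for "up to 20% data loss".

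The Statistical analysis section of the same document describes multilevel regression "with patient at level 2, using an autoregressive (AR(1)) covariance structure, fitted by maximum likelihood". The predictors are time, group and their interaction, with a squared time term considered on model fit. The primary test is the time × group coefficient for PHQ-15 from pre- to post-treatment. Imputation is done separately by arm, from time, age, gender, two screening scores, adherence and missing-data rate. Neither list contains cohort.

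The separate mediation SAP does not mention cohort either. Its section on exposure exercises, alliance and credibility reuses the primary models, so the omission carries over. It gives the trial size as 161.

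**The concern.** If 1:1 allocation holds within each cohort, cohort is a randomisation block. Differences between blocks then cancel out of the treatment contrast by design. An analysis that ignores the blocks still counts those differences as error, so it reports a wider standard error than the design has earned.

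The documents give some reason to think cohorts might differ in change. Recruitment was planned from about summer 2021 to mid-2023, so the 10-week phases cover different seasons. The Procedure section also allows recruitment to widen to other clinics, and then to advertising, if inclusion is slow. At stake is a small amount of power, not the validity of a positive result.

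**Working it through.** **1. The plan's own figure.** A two-sided, two-sample t-test with d = 0.5, α = 0.05 and 80% power needs 64 per arm. Dividing by 0.8 for data loss gives 64 / 0.8 = 80 per arm, so N = 160 reproduces. The normal approximation gives 63 per arm, then 79 per arm after inflation, total 158. Neither calculation uses blocking or a cohort variance.

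**2. Which cohort differences matter.** The test concerns a group difference in change. Cohort differences in PHQ-15 level are absorbed at patient level and drop out. Only differences in rate of change matter, so a cohort main effect alone would not help; the cohort-by-time term does the work.

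A simulation used 128 completers, 11 occasions (pre, weeks 1–9, post), exact balance within cohorts, and a t-test on patient slopes with and without cohort, with 4,000 runs per setting. The assumed true slope variance was 0.09 and the residual SD was 2. In both rows, 10% of the intercept variance was also due to cohort.

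| Cohort differences | Cohort size | Mean SE, cohort ignored | Mean SE, cohort modelled |
|---|---|---|---|
| Level only | 8 | 0.0627 | 0.0627 |
| Level only | 16 | 0.0628 | 0.0628 |
| Also 10% of true slope variance | 8 | 0.0626 | 0.0604 |
| Also 10% of true slope variance | 16 | 0.0625 | 0.0605 |

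**3. Size of the loss.** Let ρ be the share of the total variance in estimated change that is due to cohort. The documents do not give it; 2–10% is assumed. With exact balance and patient slope differences in the error term, true SE = √(1 − ρ) × reported SE. Write z = 1.960 for the two-sided 5% point, and 1.960 + 0.842 = 2.802 for the standardised effect at nominal 80% power. Then:

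- reported SE / true SE = 1 / √(1 − ρ)
- type I error, cohort ignored = 2[1 − Φ(z / √(1 − ρ))]
- power, cohort ignored = Φ(0.842 / √(1 − ρ))
- power, cohort modelled = Φ(2.802 / √(1 − ρ) − 1.960)

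| ρ (assumed) | SE ratio | Type I error | Power, ignored | Power, modelled | Gain (points) |
|---|---|---|---|---|---|
| 0 | 1.000 | 5.0% | 80.0% | 80.0% | 0 |
| 0.02 | 1.010 | 4.8% | 80.2% | 80.8% | 0.5 |
| 0.05 | 1.026 | 4.4% | 80.6% | 82.0% | 1.4 |
| 0.10 | 1.054 | 3.9% | 81.2% | 84.0% | 2.7 |

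Gains are taken before rounding. The right comparison is between the last two power columns, not with nominal 80%, because the unadjusted test already benefits from the blocking.

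**4. The denominator.** ρ is a share of total variance in estimated change, weekly measurement noise included. In the simulation, noise adds 2² / 110 = 0.036 to each patient's slope variance (110 is the sum of squared centred times 0–10). So 10% of true slope variance is 0.009 / (0.09 + 0.036) = 7.1% of the total. The formula then gives 1 / √0.929 = 1.038, against 0.0626 / 0.0604 = 1.036 simulated.

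**The case against.** The strongest reply is that no loss has been shown. The documents give no figure for cohort differences in change. Both arms receive structured online content over the same 10 weeks, and widening recruitment is only a contingency. A reader might infer that the error term is too large as a matter of fact. The documents do not support that; at ρ = 0 nothing is lost. This part of the reply stands, and the point is therefore conditional.

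Second, a reader might infer that the primary test errs on the safe side. That does not follow either. The plan states no random slope. Read literally, as a random intercept with AR(1) residuals, the model can leave patient differences in slope out of the standard error. If true slope differences make up 30–70% of the variance of patient slope estimates, and cohort explains 10% of them (all assumed), the reported standard error is about 8–26% too small and type I error about 7–15%. That is a separate matter from cohort and far larger. It means that the conservative direction shown in the working holds only if slope differences are otherwise in the error term.

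Third, exact balance is inferred. The phrase about even numbered cohorts is read here as cohorts of even size, and the later N of 161 is odd, so not every cohort can have contributed an even number of patients. This loosens the formula but leaves the principle intact.

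**Conclusion.** The plan randomises by cohort and then leaves cohort out of both the analysis and the imputation model. That much is in the text. The consequence is conditional on cohorts differing in rate of change, on patient slope differences being in the error term, and on near-exact balance. Under those conditions and an assumed ρ of 2–10%, the standard error is 1–5% too wide, type I error is about 4.8–3.9%, and 0.5–2.7 points of power are forgone. If cohorts differ only in level, the loss is zero.

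A reader might infer that ignoring the cohorts inflates false positives or undermines the sample size. The documents support neither: omitting balanced blocks cannot raise type I error by that route, and N = 160 reproduces without them. This is an optional refinement.

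**What to change.** State the number and size of cohorts and how 1:1 allocation was kept within them. Add cohort and cohort-by-time to the primary model, as random terms if cohorts are small, and keep the time × group test and N as they are. Add cohort to the imputation predictors so that the two models agree. If the primary analysis is already fixed, report this as a sensitivity analysis.

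The cost is two model terms and one imputation predictor. It requires cohort membership to be in the dataset, which randomising by cohort makes likely but the documents do not state. Fixed terms use a few degrees of freedom: cohorts of 16 among 128 completers make 8 cohorts. In the simulation with no cohort variance this cost no visible power (79.9% without cohort, 80.1% with it). A random term may estimate to zero, in which case the result is in effect that of the planned model.

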- g) Not severe psychiatric condition or suicidal ideation

Exposure-based treatment vs. standardized education for distress related to somatic symptoms
Study protocol intended for peer review

- h) No clear medical risk in taking part in exposure-based treatment (e.g., pregnancy) and somatic condition, or treatment for somatic condition, does not make treatment unfeasible
- i) Continuous psychotropic medication (antidepressants, anticonvulsants, mood-stabilizers, antipsychotics) either non-existent or stable since at least 4 weeks, and expected to remain stable over the main phase of the trial
- j) Not severe alcohol or substance use disorder likely to interfere with treatment
- k) Not planned absence for more than 1 week during the intended main phase
- l) Complete pre-treatment assessment

Instruments

Psychiatric assessment is based on the Mini-International Neuropsychiatric Interview (MINI (18)) and Health Preoccupation Diagnostic Interview (HPDI (19)). Primary outcome measure is somatic symptom burden as assessed using the Patient Health Questionnaire 15 (PHQ-15 (16)). Secondary outcomes are: symptom preoccupation (SSD-12 (20); SYMPS-prel), general anxiety (GAD-7 (21)), depression (PHQ-9 (22)), disability (WHODAS 2 (23)), credibility and expectancy (C/E scale (24)), relation with the therapist (WAI-6, (25)), client satisfaction (CSQ-8 (26)), negative effects (free-text questions), quality of life (EQ-5D (27)), and societal resource use (TIC-P (28)). Health anxiety (HAI-14, (29)) and alcohol/drug use (AUDIT, DUDIT (30, 31)) are assessed for the purpose of screening only. Eleven questions concerning the basis of subjective somatic symptom burden in terms of symptom severity, disability, and emotional components will also be administered at baseline so as to facilitate the interpretation of the PHQ-15.

[figure not shown]

Figure 1. Schematic overview of participant flow

Procedure

We aim to recruit Swedish adults with recurrent distress related to somatic symptoms and an interest in psychological treatment. Patients will be referred via regular services including

Exposure-based treatment vs. standardized education for distress related to somatic symptoms
Study protocol intended for peer review

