After having completed the screening, applicants are contacted for a psychiatric assessment (primarily the MINI) and eligibility interview with a mental health clinician. As is routine practice at the clinic, this may be conducted face-to-face, via telephone, or via a secure video conferencing service. As is routinely done in the primary care clinic, the patient’s general practitioner is consulted whenever further medical evaluation is deemed necessary. Applicants who do not meet eligibility criteria a-k are excluded and referred to routine care, at the clinic if possible, and in accordance with regional healthcare guidelines. Applicants who meet eligibility criteria a-k are encouraged to complete the pre-treatment assessment. Those who do so are randomized (1:1) to flexible internet-delivered exposure-based treatment or the education control and are thereby included as participants in the trial. The subsequent 10 weeks constitute the main phase of the trial during which key measures are administered on a weekly basis (Table 1). At the end of the main phase follows the post-treatment assessment. Follow-up assessments follow 6 and 12 months after therapy.

Table 1. Key outcome measures and assessment points

Questionnaire	Outcome	Reference	SN	PRE	WK	POST	6MFU	12MFU
PHQ-15 (prim.)	Somatic symptoms	(16)	x	x	x	x	x	x
SSD-12	Symptom preoccupation	(20)	x	x	x	x	x	x
SYMPS-prel	Symptom preoccupation	Prel. version	x	x	x	x	x	x
GAD-7	Anxiety	(21)		x		x	x	x
PHQ-9 ^a	Depression	(22)	x	x		x	x	x
WHODAS 2.0	Disability	(23)	x	x		x	x	x
HAI-14	Health anxiety	(29)	x					
AUDIT, DUDIT	Alcohol, drug use	(30, 31)	x					
C/E scale	Credibility/expectancy	(24)			w. 3			
WAI-6	Relationship w. therapist	(25)			w. 3			
CSQ-8	Client satisfaction	(26)				x		
EQ-5D	Health-rel. quality of life	(27)		x		x	x	x
TIC-P	Resource use	(28)		x		x	x	x

12MFU = 12-month follow-up, 6MFU = 6-month follow-up, POST = post-treatment, PRE = pre-treatment (i.e., end of main phase), SN = screening, WK = weekly assessment (main phase week 1-9)

a) Suicidality item administered each week; patients contacted if flagged and referred to routine care as needed.

Data management

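### The imputation predictors include no PRE, weekly or POST score and no patient level is stated; under some readings the time-by-group estimate is biased if dropout depends on response differently by arm

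*Combined protocol and SAP*

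**What the plan says.** The Statistical analysis section of the protocol reads: "Multiple imputation will be based on the following predictors: time, age, gender, screening somatic symptoms, screening symptom preoccupation, treatment adherence, and missing data rate". It continues: "This will be done separately for each condition (exposure vs. control) so as to maintain group-specific interactions". Of the seven predictors, two are symptom scores, both from screening. Whether the imputation is single-level or two-level, and in long or wide format, is not stated.

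A patient level appears only for the analysis model, described as "with patient at level 2, using an autoregressive (AR(1)) covariance structure, fitted by maximum likelihood". The primary test is the time-by-group coefficient "pertaining to a group difference in average change in the PHQ-15 over the main phase of the trial, i.e., from pre- to post-treatment".

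The trial collects more than the list uses. Eligibility criterion l is "Complete pre-treatment assessment", so every randomized patient has a PRE score. Table 1 of the protocol shows PHQ-15, SSD-12 and SYMPS-prel at PRE, weeks 1 to 9 and POST. GAD-7, PHQ-9 and WHODAS 2.0 are scored in the main phase only at PRE and POST, and GAD-7 is not given at screening. Design and power allows for "and up to 20% data loss". The separate mediation SAP describes no imputation.

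**The concern.** Once a patient has left, the best guide to the missing PHQ-15 scores is that patient's own course so far, and the list leaves it out. A patient who was not improving is filled in along the trend of the whole arm. The plan imputes by arm to preserve arm-specific trends; the same reasoning applies to patient-specific trends.

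At stake is the primary estimate. If poor responders leave exposure, the benefit of exposure is overstated; if good responders leave exposure, it is understated. The wording also leaves an analyst free to choose among a single-level model, a random-intercept model and a random-slope model. All three fit the text, and they do not give the same answer.

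**Working it through.** **1. The plan's own figure.** Inputs from Design and power: d = 0.5, 80% power, alpha 0.05 (taken as two-sided), 1:1 allocation, loss up to 20%. Per arm, n = 2(1.96 + 0.84)²/0.5² = 62.7, so 63; the t-test version gives 64. Then 2 × 64/0.8 = 160, the stated N. The 20% loss is therefore the natural case to examine.

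**2. Why the trend is lost.** Let patient i have score y = (β0 + u_i) + (β1 + b_i)·t + e, where b_i is the patient's departure from the arm's average change. A single-level imputation within an arm is y* = α + γ·t + δ'x_i + ε. The covariates x_i move the level, while γ is common to the arm and b_i does not appear. A patient random intercept adds a_i to the level and leaves γ common. Observed scores are untouched; only missing cells are affected.

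**3. Size, first simulation.** From the documents: 80 per arm and 11 occasions (PRE, weeks 1 to 9, POST). Assumed: endpoint SD about 5, so a true difference of 0.5 × 5 = 2.5 points (mean change −4.0 in exposure, −1.5 in control); SD of 10-week change 2 to 3.5; dropout log-odds 0.15 or 0.3 per PHQ-15 point of last observed change; monotone dropout. Runs: 500 replicates, 20 imputations, Monte Carlo SE at most 0.014. Listed predictors, single-level, by arm, 20% loss:

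| Dropout | Estimate (truth −2.50) |
|---|---|
| Random | −2.50 |
| Same mechanism and rate in both arms | −2.49 to −2.50 |
| Same mechanism, 25% exposure and 15% control loss | −2.52 to −2.61 |
| Poor responders leave exposure only | −2.54 to −2.74 |
| Good responders leave exposure only | −2.21 to −2.44 |
| Poor leave exposure, good leave control | −2.59 to −3.02 |
| Good leave exposure, poor leave control | −1.96 to −2.39 |

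Subtracting −2.50, one-arm dependence gives −0.04 to −0.24 or +0.06 to +0.29. Opposite dependence gives −0.09 to −0.52 or +0.11 to +0.54. At 10% loss the absolute bias is 0.02 to 0.16 and 0.05 to 0.29. Wide-format imputation with own scores (time and missing data rate omitted) gave −2.49 to −2.51 in every scenario.

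**4. Second simulation, different assumptions.** True difference −2.25, slope SD 3, loss about 18 to 25% per arm, maximum likelihood with random intercept and AR(1). The complete-data estimate was −2.21, Monte Carlo error about 0.03.

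| Dropout | Listed, single-level | Own earlier scores added | No imputation |
|---|---|---|---|
| Poor leave exposure only | −2.41 | −2.23 | – |
| Poor leave exposure, good leave control | −2.56 | −2.24 | −2.50 |
| Reverse | −1.91 | −2.23 | −1.98 |

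Against complete data, the list shifts the estimate by −0.20, −0.35 and +0.30. Without imputation the last two shifts are −0.29 and +0.23, that is 0.29/0.35 = 83% and 0.23/0.30 = 77% of the shift under the list. With slope SD set to 0, the bias was 0.04 or less.

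**5. Two-level imputation** (first simulation, middle variance set, log-odds 0.3, 300 replicates, 10 imputations). With a random intercept only: −2.67 (poor leave exposure), −2.27 (good leave exposure), −2.86 (opposite). With random intercept and slope: −2.44, −2.52, and −2.39 and −2.58 for the two opposite patterns.

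**6. Missing data rate in wide format.** Under purely monotone dropout, nearly all patients with later scores have a rate near zero, so its coefficient is extrapolated. Keeping it gave −2.08, −3.16 and −1.50 (poor leave exposure, good leave exposure, opposite), with an SE of 0.90 against 0.68 under random dropout. With an assumed 10% of single questionnaires also skipped, it gave −2.44, −2.66 and −2.24 (Monte Carlo SE 0.04), with an SE of 0.81 against 0.67.

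**The case against.** The plan does not say that the imputation is single-level. In a two-level imputation the patient is the cluster identifier and would not appear among the predictors, so this list could also describe such a model. That stands: the text shows an unspecified model, not a demonstrated error. It does not settle the matter, because a random intercept alone leaves the bias in place and nothing in the text promises a random slope.

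The bias needs two conditions together: patients who differ in true change, and dropout that depends on response differently by arm. The documents give no slope SD and no dropout mechanism. They do give some reason for care. The protocol's discussion of risks expects short-term symptom increases, but few or no adverse events in control, and control patients are offered exposure after POST. This makes arm-specific dropout possible, not established.

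The gain is also limited. With one-arm dependence, RMSE was about unchanged by the fix (0.66 to 0.66 and 0.66 to 0.64). It fell clearly, from 0.73 to 0.66, only under opposite dropout.

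A reader might infer that the imputation is the culprit and should be dropped. The no-imputation results in step 4 do not support this: a random-intercept and AR(1) model, the natural reading of the planned analysis, shows most of the same shift. Nor is missing data rate simply harmful. In a single-level model it gives some protection: without it, the second simulation gave −2.63 and −1.83 under opposite dropout, against −2.56 and −1.91 with it.

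**Conclusion.** The point holds as a gap in specification with a conditional consequence. Used as written in a single-level model, or with a patient random intercept only, the list replaces the patient's own trend by the arm's. The resulting bias is small to moderate: 0.3/2.5 = 12% of the assumed effect at the top of the one-arm range and 0.5/2.5 = 20% at the top of the opposite range, both at the full 20% loss. These sizes rest on assumed variances and dropout strength.

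It would go too far to conclude that the primary result will be biased. The documents neither state the single-level model nor predict the dropout that would be needed. Coverage is not part of this conclusion: the second simulation's random-intercept model covered only 86% even with complete data, because it had no random slope, which is a separate matter.

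**What to change.** State the imputation model in one or two sentences. Impute by arm in wide format, adding to the listed patient covariates the patient's own PRE, weekly and POST scores of the same scale, or own PRE and POST for GAD-7, PHQ-9 and WHODAS. Time is then not a covariate.

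For the weekly scales only (PHQ-15, SSD-12, SYMPS-prel), a two-level imputation with a patient random intercept and a random slope for time is an acceptable alternative. It is not identified for scales with only PRE and POST.

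Check whether missing data rate can be estimated in the wide model, and leave it out if nearly all patients with later scores have a rate near zero. This is a caution that depends on the observed pattern of missing data, not a fixed instruction.

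The cost is a larger imputation model with about 80 patients per arm and slightly more code. The mean SE was 0.68 to 0.69 against 0.61 to 0.63, about 10% wider. No new data are needed.
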